##### **2. Hematologic dose limiting toxicity**

- Grade 3 thrombocytopenia with Grade 3 or 4 hemorrhage
- Grade 4 thrombocytopenia (platelet count  $<25,000/\text{mm}^3$ ) or
- Grade 4 neutropenia.

## 9.0 DOSE MODIFICATIONS FOR ADVERSE EVENTS

**The study PIs must be notified of any dosage modification.**

- 1. Dose modifications for hematological toxicity** (Of note, such adverse events have been observed in patients with CML (chronic myelogenous leukemia), likely contributed by concurrent morbidities).
  - If a patient experiences Grade 3 neutropenia (ANC $<1000$ ) or Grade 3 thrombocytopenia (platelets  $<50,000/\text{mm}^3$ ) with or without Grade 1 or 2 non-CNS hemorrhage, the treatment will be withheld. Counts should be checked twice weekly during this time. If the toxicity resolves to meet on study parameters within 14 days of drug discontinuation, the patient may resume treatment with the dose reduced as mentioned in Section 6.1. Treatment should resume 14 days from drug discontinuation even if toxicity has resolved before 14 days in order to allow for a full 2-week rest period before resuming drug.
  - If a patient experiences Grade 1 CNS hemorrhage or Grade 3 or  $>$  non-CNS hemorrhage, the treatment will be withheld. Treatment will not be resumed and the participant will discontinue study drug permanently.
  - If toxicity does not resolve to meet on study parameters within 14 days of drug discontinuation, the patient must be removed from protocol therapy.
  - If dose-limiting toxicity recurs in a patient who has resumed treatment at the reduced dose (maximum of 2 dose reductions allowed), the patient must be removed from protocol therapy.
  - Myeloid growth factors will not be used on study.
- 2. Dose modifications for non-hematological toxicity.**
  - If a patient experiences non-hematologic DLT as defined in Section 8, the treatment will be withheld. If the toxicity resolves to meet on study parameters within 14 days of drug discontinuation, the patient may resume treatment with the dose reduced as mentioned in Section 6.1 (see Appendix A). Treatment should resume 14 days from drug discontinuation even if toxicity has resolved before 14 days. Doses reduced for toxicity will not be re-escalated, even if there is minimal or no toxicity with the reduced dose.
  - If toxicity does not resolve to meet on study parameters within 14 days of drug discontinuation, the patient must be removed from study.
  - If dose-limiting toxicity recurs in a patient who has resumed treatment at the reduced dose level, the patient must be removed from protocol therapy.
  - Dose modifications for left ventricular systolic dysfunction: Left ventricular systolic dysfunction will be graded according to CTCAE criteria but will also take into account absolute changes in shortening fraction.

Grade 1 left ventricular systolic dysfunction: Continue imatinib at current dose level and repeat echocardiogram in 30 days.

Grade 2 left ventricular systolic dysfunction OR  $>8$  absolute percentage point decrease in shortening fraction: hold study drug and repeat echocardiogram in 7 days. If repeat echocardiogram confirms toxicity, patient will be taken off-protocol therapy and should be referred to a cardiologist. If repeat echocardiogram does not confirm toxicity, patient may restart therapy with repeat echocardiogram 14 days after restart. If any two echocardiograms demonstrate Grade 2 dysfunction OR  $>8$  absolute

percentage point decrease in shortening fraction, patients will be taken off-protocol therapy and should be referred to a cardiologist.

≥Grade 3 left ventricular systolic dysfunction: Off-protocol therapy. Referral to cardiologist.

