#### **8.0 DEFINITION OF DOSE-LIMITING TOXICITY (DLT)**

DLT will be defined as any of the following events that are possibly, probably, or definitely attributable to imatinib.

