##### **1. Non-hematologic dose-limiting toxicity**

- Any Grade 4 non-hematologic toxicity
- Any Grade 3 non-hematologic toxicity with the specific exception of:
  - Grade 3 ALT that return to levels that meet initial eligibility criteria within 7 days of study drug interruption and that do not recur upon rechallenge with study drug. Note: For the purposes of this trial the ULN for ALT is defined as 45 U/L.
  - Grade 3 AST
  - Grade 3 fever or infection <5 days duration
  - Grade 3 hypophosphatemia, hypokalemia, hypocalcemia or hypomagnesemia responsive to oral supplementation within 14 days of initiating supplementation
  - Asymptomatic Grade 3 elevations in amylase or lipase resolving to <Grade 1 within 7 days of study drug interruption and that do not recur upon re-challenge with study drug
- Grade 2 or greater left ventricular systolic dysfunction OR an absolute decrease in shortening fraction of 8 percentage points from baseline.
- Grade 2 allergic reactions that necessitate discontinuation of study drug will not be considered a dose limiting toxicity.
- Any Grade 2 non-hematological toxicity that persists for  $\geq 7$  days and is considered sufficiently medically significant or sufficiently intolerable by patients that it requires treatment interruption.
- Any adverse event requiring interruption of study drug for  $>7$  days or which recurs upon drug re-challenge.

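### The permanent-stop rule for bleeding in Section 9 names Grade 1 CNS hemorrhage without an 'or higher', so as literally worded it leaves out the worse grades

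*Combined protocol and SAP*

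**What the plan says.** Section 9.0, part 1 (hematological toxicity) contains two adjacent bullets that deal with bleeding.

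- The first begins "If a patient experiences Grade 3 neutropenia (ANC" and gives a cut-off of below 1000. It also covers Grade 3 thrombocytopenia, with or without non-CNS hemorrhage of Grade 1 or 2. Drug is held and may be resumed at a reduced dose if the toxicity resolves within 14 days.
- The second begins "If a patient experiences Grade 1 CNS hemorrhage or Grade 3 or" and continues with a greater-than sign and the words for non-CNS hemorrhage. Its consequence is absolute: "Treatment will not be resumed and the participant will discontinue study drug permanently".

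In the second bullet the open-ended grade is attached to the non-CNS term. The CNS term is a bare Grade 1. Elsewhere the protocol writes the floor out when it wants one, as in Section 8.0: "Grade 2 or greater left ventricular systolic dysfunction".

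**The concern.** The bullet is a mandatory patient-safety stop, applied at two sites to 20 treated patients. Taken word for word, it ends treatment for the mildest CNS bleed and does not name any worse one. A site that continued or restarted drug after a Grade 2 CNS bleed would not clearly have broken the protocol. The question is whether another rule closes the gap, and how much depends on it if none does.

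**Working it through.** No arithmetic is involved, and the plan states no figure to reproduce. The check sets the bullet beside every other rule that could stop drug for CNS hemorrhage.

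**Step 1: what each reading covers.** Inputs: Grades 1 to 4 and the trigger in Section 9.0, part 1.

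| CNS hemorrhage | Bare Grade 1, as written | Grade 1 as a floor |
|---|---|---|
| Grade 1 | permanent stop | permanent stop |
| Grade 2 | not named | permanent stop |
| Grade 3 | not named | permanent stop |
| Grade 4 | not named | permanent stop |

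Literal: 1 of 4 grades. Floor: 4 of 4. The readings differ at Grades 2, 3 and 4. This counts what the wording covers; it does not estimate events.

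**Step 2: does the protocol's usage settle the reading?** It does not. In the neutropenia bullet the numeric cut-off makes a bare Grade 3 work as a floor. In the left ventricular rules at the end of Section 9.0, bare Grades 1 and 2 are single grades and the top step carries its own sign for Grade 3 and above. Within the bleeding sentence itself, one term has the floor and the other does not.

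**Step 3: is Grade 2 stopped by another rule?** Only conditionally. The DLT definition applies under an attribution condition: "DLT will be defined as any of the following events that are possibly, probably, or definitely attributable to imatinib". Within it, Section 8.0 offers three routes for a Grade 2 event:

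- it lasts at least 7 days and "is considered sufficiently medically significant or sufficiently intolerable by patients that it requires treatment interruption";
- it requires interruption for more than 7 days;
- it recurs on re-challenge.

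Section 6.1 stops drug permanently if an event has not come down to Grade 2 or baseline within 14 days. A Grade 2 bleed meets that test from the start.

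**Step 4: are Grades 3 and 4 stopped by another rule?** Not unconditionally. The hematologic DLT list mentions hemorrhage only in combination, "Grade 3 thrombocytopenia with Grade 3 or 4 hemorrhage", and does not refer to the CNS. If a CNS bleed is instead handled as a non-hematologic toxicity, Grades 3 and 4 are DLTs when at least possibly attributable to imatinib, since hemorrhage is not among the listed Grade 3 exceptions. Section 9.0, part 2 then applies: "If a patient experiences non-hematologic DLT as defined in Section 8, the treatment will be withheld". Dosing may resume at a reduced dose, after a full 14-day rest, if the event has resolved to on-study parameters within 14 days; otherwise the patient is removed. The bleeding bullet in part 1 carries no attribution condition, so a severe CNS bleed judged unrelated to imatinib would not be a DLT either. Section 1.0 lists stroke among the complications of the disease, so such a judgment is conceivable.

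**Step 5: general removal rules.** The remaining stops depend on non-resolution or recurrence (Sections 6.1 and 9.0) or on the physician's judgment (Section 13.0). None orders a stop at onset for CNS hemorrhage of Grade 2 or higher.

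**The case against.** The strongest reply is that the context already says what is meant. The bullet directly above uses bare grades as floors, and must do so: Grade 4 neutropenia and Grade 4 thrombocytopenia are hematologic DLTs, yet part 1 has no separate hold rule for them and part 2 holds drug only for non-hematologic DLTs. That same bullet limits hold-and-resume to Grade 1 or 2 bleeding outside the CNS. Read as a pair, the bullets send milder non-CNS bleeds to a hold, and severe non-CNS bleeds and any CNS bleed to a permanent stop. The left ventricular rules are a stepwise ladder and so a weaker guide. All of this stands as evidence of intent. It does not repair the sentence, which marks the floor on one term and omits it on the other.

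A reader might infer that the protocol permits restart at day 14 after a Grade 3 or 4 CNS bleed. The documents do not support that as a flat permission. It requires handling as a non-hematologic DLT, which is an assumption because the explicit hemorrhage rules sit under hematologic headings in both Section 8.0 and Section 9.0. It also requires attribution to imatinib and resolution to on-study parameters within 14 days. If those parameters mean the entry criteria, the Karnofsky floor of 80 and the exclusion for severe or uncontrolled disease would often block restart.

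The objection is also right that little would probably change in practice. Suspected DLTs and serious events go to the principal investigator within 24 hours (Section 7.0), dose modifications must be notified (Section 9.0), and the physician may end therapy (Section 13.0).

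Finally, a sign could have been lost before Grade 1 when the PDF was read. That cannot be excluded, but the greater-than sign later in the sentence survived, as did the sign in the left ventricular rules, and nothing marks a gap.

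**Conclusion.** The point holds as a wording error in an operative safety rule. As literally worded, the unconditional stop covers Grade 1 CNS hemorrhage and omits Grades 2 to 4, and no other rule supplies an unconditional stop for them. The intended rule is almost certainly Grade 1 or higher, and the practical risk is low.

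The documents give no rate of CNS hemorrhage, and entry requires platelets of at least 100,000/µL, so no number of affected patients can be stated. It would go too far to say that the protocol deliberately treats worse bleeds more leniently, or that patients would in practice be restarted. The DLT stopping boundary in Section 15.3 is not affected, because it counts DLTs as defined in Section 8.0 and does not use this bullet. Sample size, power, alpha and endpoints are unchanged. This is a minor but real correction.

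**What to change.** Reword the trigger to: Grade 1 or higher CNS hemorrhage or Grade 3 or higher non-CNS hemorrhage. The sponsor's clinicians should confirm that this is the intended threshold. Optionally, add one sentence saying that this bullet takes precedence over the resume provisions in Section 6.1 and Section 9.0, part 2.

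The cost is two words on the CNS term, and a word in place of a symbol on the non-CNS term, in a short written amendment. Section 19.1.1 requires approval by all principal investigators, and IRB approval where subject safety is significantly affected; a safety stop should be treated as falling under that. There are no added visits, tests, patients or analyses.

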See Section 8 and 9 for dose-limiting toxicities and dose reductions/modifications. If the toxicity resolves to meet study parameters within 14 days of drug discontinuation, the patient may resume treatment with the dose reduced by from 340 mg/m^2 to 260 mg/m^2. Treatment should resume 14 days from drug discontinuation even if toxicity has resolved before 14 days in order to allow for a full 2-week rest period before resuming drug. Subjects who fail to recover to a <= grade 2 or baseline within 14 days of AE onset will permanently discontinue study drug. This does not include the following AEs: nausea and fatigue (does not require dose reduction or discontinuation). Upon restarting drug, the dose will be reduced to 260 mg/m^2 (see table in Appendix A) and not re-escalated in subsequent cycles. A maximum of 2 dose reductions (340 mg/m^2 to 260 mg/m^2 to 200 mg/m^2) will be allowed before permanent discontinuation of study drug.

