## **11.0 EVALUATIONS/MATERIAL AND DATA TO BE ACCESSIONED**

Subjects will be prescreened for potential eligibility prior to initial clinic visit. All entry/eligibility laboratory and imaging studies will be performed at or within 2 weeks of the initial visit. Baseline EKG to rule-out prolonged QTc, and if needed, echocardiogram, is required within 2 weeks of starting protocol therapy. If eligibility studies are drawn but the participant was not able to be enrolled/initiate study drug (e.g. hospitalized) in this timeframe, all eligibility laboratory studies will need to be repeated. EKG and ECHO do not need repeated unless there are new clinical concerns. Each study visit will occur approximately 4 weeks (+/- 1 week) after the previous.

STUDIES TO BE OBTAINED	Baseline	2 Weeks	1 Month	2 Months	3 Months	4 Months	5 Months	6 Months	1 month Off Study
Phone Assessment (Weekly)			X	X					
History	X		X	X	X	X	X	X	X
Physical exam with vital signs	X		X		X			X	X
Height, weight, BSA	X		X	X	X	X	X	X	X
Performance Status	X		X	X		X	X		
CBC/platelet with differential, Reticulocyte Count	X	X	X	X	X	X	X	X	X
HPLC or Hemoglobin EP	X								
Ektacytometry, OxygenScan, F% correlation, Blood Viscosity#	X		X		X			X	X
% ISCs (irreversibly sickled cells)	X		X		X			X	X
D-dimer	X		X		X			X	X
Urine Pregnancy test (female)	X		X		X			X	
CMP^, Mag, Phos, Uric Acid, Amylase, Lipase and tryptase	X		X		X			X	X
Biochemical Analysis Sample	X		X		X			X	X
EKG*	X								X
Echocardiogram*	X								
Patient Pain Journal			X	X	X	X	X	X	X
Concomitant Medication Assessment	X	X	X	X	X	X	X	X	X

**Table 2.** Studies to confirm eligibility and monitor safety and efficacy on imatinib

\*During study treatment, monitor for signs and symptoms of arrhythmia and for edema and fluid retention that may cause congestive heart failure. Obtain EKG/echocardiogram and cardiology consult as clinically indicated.

#Blood samples for these studies to be sent to Cincinnati

[figure not shown]
^CMP should include Albumin, Alkaline phosphatase, ALT (SGPT), AST (SGOT), BUN, Calcium, Chloride, Carbon Dioxide, Creatinine, Glucose, Potassium, Sodium, Total Bilirubin, Total Protein, and a calculation of eGFR.

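### A shortening-fraction fall of exactly 8 points is a cardiac DLT in Section 8 but falls outside Section 9's left ventricular rule, and the baseline value needed to score it is not guaranteed

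*Combined protocol and SAP*

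**What the plan says.** Section 8 lists as a non-hematologic DLT, when at least possibly attributable to imatinib, "Grade 2 or greater left ventricular systolic dysfunction OR an absolute decrease in shortening fraction of 8 percentage points from baseline". Section 15.3 counts DLTs by that definition.

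Section 9, item 2, then gives two sets of instructions.

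- **General rule.** For any non-hematologic DLT of Section 8, drug is withheld. If the toxicity resolves within 14 days, "the patient may resume treatment with the dose reduced as mentioned in Section 6.1 (see Appendix A", with the restart on day 14.
- **Left ventricular rule.** This is a later bullet in the same item. For Grade 2 dysfunction or a fall of more than 8 points, it directs, after the >8 threshold: "absolute percentage point decrease in shortening fraction: hold study drug and repeat echocardiogram in 7 days". Next: "If repeat echocardiogram confirms toxicity, patient will be taken off-protocol therapy and should be referred to a cardiologist". Otherwise: "If repeat echocardiogram does not confirm toxicity, patient may restart therapy with repeat echocardiogram 14 days after restart". The >8 threshold appears again in the sentence on any two abnormal echocardiograms. Grade 3 or worse ends protocol therapy at once.

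On the baseline, Section 11 states: "Baseline EKG to rule-out prolonged QTc, and if needed, echocardiogram, is required within 2 weeks of starting protocol therapy". The same section also states: "All entry/eligibility laboratory and imaging studies will be performed at or within 2 weeks of the initial visit". Table 2 marks an echocardiogram at baseline. Criterion 5d in Section 5.2.1 requires either shortening fraction or ejection fraction above the institutional lower limit of normal.

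**The concern.** A DLT criterion and the rule that manages it should share one threshold. Here they differ at a single whole-number value, and echocardiogram results may well be reported in whole percents. At that value the patient follows a path written for toxicities in general, which allows a restart at a lower dose. One point higher, the same patient is re-imaged at 7 days and stopped if the fall is confirmed.

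Two further gaps bear on the same event. The plan does not say which rule governs when both apply, or at what dose a patient restarts after an unconfirmed repeat, so the two sites could act differently. The criterion is also a change from baseline, and the plan does not ensure that the baseline shortening fraction exists.

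**Working it through.** **1. Which rule is triggered.** Take an attributable fall with dysfunction below Grade 2, and read Section 8's wording as 8 or more, its natural sense.

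| Fall in shortening fraction | DLT (Section 8) | General rule (Section 9) | Left ventricular rule (Section 9) |
|---|---|---|---|
| Less than 8 points | No | No | No hold |
| Exactly 8 points | Yes | Yes: withhold | No hold |
| More than 8 points | Yes | Yes: withhold | Yes: hold and repeat at 7 days |

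The mismatch is confined to the middle row. If Grade 2 dysfunction is also present, the left ventricular rule applies whatever the size of the fall.

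**2. What the two rules do.**

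| Step | General rule | Left ventricular rule |
|---|---|---|
| Drug | Withheld | Held |
| Repeat echocardiogram | No time specified | At 7 days |
| Abnormality persists | Removed if not resolved within 14 days | Off therapy once the repeat confirms it |
| Abnormality gone | Resume on day 14, dose reduced | May restart; dose not named; another echocardiogram 14 days later |

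**3. Size of the unnamed restart dose.** Inputs are the 340 and 260 mg/m² tables in Appendix A. The plan gives no distribution of body surface area (BSA), so I assume 1.40 m² and above for these adults.

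| BSA (m²) | 340 mg/m² | 260 mg/m² | Difference |
|---|---|---|---|
| 1.40–1.44 | 500 mg | 350 mg | 150 mg (150/500 = 30%) |
| 1.45–1.54 | 500 mg | 400 mg | 100 mg (20%) |
| 1.55–1.63 | 550 mg | 400 mg | 150 mg (27%) |
| 1.64–1.69 | 550 mg | 450 mg | 100 mg (18%) |
| 1.70–1.82 | 600 mg | 450 mg | 150 mg (25%) |
| 1.83–2.01 | 600 mg | 500 mg | 100 mg (17%) |
| 2.02 and above | 600 mg | 550 mg | 50 mg (50/600 = 8%) |

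If restarting means the dose that was held, it is 50 to 150 mg/day higher than under the general rule.

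**4. Baseline value.** The Section 8 criterion is baseline shortening fraction minus the on-treatment value. Table 2 schedules the echocardiogram, but Section 11's text makes it conditional, and criterion 5d can be met with ejection fraction alone. A patient can therefore be eligible with no recorded shortening fraction. The plan does not say how many would be affected; the possible range is 0 to 20.

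**5. Power, for the cost of the fix.** Inputs from Section 15.1: difference 70,000; SD 75,000; correlation 0.5; two-sided alpha 0.05/5 = 0.01; n = 20.

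- SD of the paired difference = 75,000 × √(2 × (1 − 0.5)) = 75,000.
- Noncentrality = (70,000/75,000) × √n, with n − 1 degrees of freedom.
- n = 20: power 89.0%, which reproduces the stated 89%.
- n = 19: 86.6%. n = 18: 83.9%.

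**The case against.** The strongest reply is that Section 9 already works when read sensibly. The left ventricular text is a bullet in the same item as the general rule and gives grade-by-grade instructions, so the ordinary reading is that the specific governs the general. Resolution of a shortening-fraction fall can hardly be judged without another echocardiogram, and the footnote to Table 2 calls for imaging and a cardiology consult when clinically indicated. The baseline echocardiogram is in Table 2. Most of this stands. What it leaves open is the exact 8-point case, which the special rule does not reach, along with the unwritten precedence, the unnamed dose and the missing guarantee of a baseline shortening fraction.

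A reader might infer more than the documents support:

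- *That Section 9 takes no action at 8 points.* The general rule withholds drug for every Section 8 non-hematologic DLT, including this one.
- *That the plan sends confirmed cardiac toxicity back to treatment.* That needs the general rule to prevail over the left ventricular bullet, which is the less natural reading. The defect is a missing precedence sentence.
- *That Section 6.1 treats Grade 2 as recovery.* The sentence is "Subjects who fail to recover to a <= grade 2 or baseline within 14 days of AE onset will permanently discontinue study drug". It says when drug must be stopped for good. Permission to restart is given separately in 6.1 and requires the toxicity to resolve to study parameters.
- *That the stopping boundary is distorted.* Section 15.3 counts by Section 8, so an attributable fall of exactly 8 counts already. Differences in later handling do not alter that.
- *That no baseline echocardiogram is planned.* Table 2 and the eligibility imaging sentence say otherwise. The conflict is with the conditional phrase in Section 11.

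**Conclusion.** The point holds as a minor inconsistency in safety handling. One value, a fall of exactly 8 points below Grade 2, is a counted DLT that the dedicated cardiac rule misses. For that patient the difference is between a possible reduced-dose restart from day 14 and a 7-day repeat with permanent discontinuation if confirmed. The restart dose after an unconfirmed repeat is open by 50 to 150 mg/day, assuming a BSA of at least 1.40 m². The baseline shortening fraction may be absent in an unknown number of patients.

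The plan gives no frequency for such falls. On-treatment echocardiograms are done only when clinically indicated, so few cases may come to light. The DLT count, the stopping boundary and the planned analysis are not affected by the inconsistency itself. The conclusion rests on reading Section 8's wording as 8 or more.

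**What to change.** 1. Write *a decrease of 8 percentage points or more from baseline* in Section 8 and in both places in Section 9's left ventricular rule.
2. State in Section 9 that the left ventricular rule overrides the general non-hematologic rule for left ventricular events, and name the restart dose after an unconfirmed repeat. Adopt this together with item 1: precedence alone would leave a fall of exactly 8 outside the hold.
3. Delete the words *if needed* in Section 11 and require shortening fraction to be recorded on the baseline echocardiogram already in Table 2.

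The cost is small. Drug is already withheld at exactly 8 points, so what is new for those patients is the 7-day repeat and leaving therapy if the fall is confirmed. If it is not confirmed, they restart under the left ventricular rule at the dose now named. Section 14 takes patients off study 30 days after the last dose, so someone stopped before about month 5 would have no month-6 sample. One lost pair lowers power from 89.0% to 86.6%, and two lower it to 83.9%. Item 3 adds no scheduled test beyond Table 2.

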### Imatinib 200mg/m^2/day

Body Surface Area (m  )	Total Daily Dose (Rounded to Nearest 50mg)	Recommended Administration
≤ 0.37	50 mg	½ x 100mg tablet once daily
0.38 – 0.62	100 mg	1 x 100mg tablet once daily
0.63 – 0.87	150 mg	1 ½ x 100mg tablet once daily
0.88 – 1.12	200 mg	2 x 100mg tablet once daily
1.13 – 1.37	250 mg	2 ½ x 100mg tablet once daily
1.38 – 1.62	300 mg	3 x 100mg tablet once daily
1.63 – 1.87	350 mg	3 ½ x 100mg tablet once daily
1.88 – 2.12	400 mg	4 x 100mg tablet once daily
2.13 – 2.37	450 mg	4 ½ x 100mg tablet once daily
≥ 2.38	500 mg	5 x 100mg tablet once daily

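### Sections 6.1, 8 and 9 conflict on a non-hematologic DLT that returns at the first reduced dose, and on dose reduction and removal for attributable Grade 3 nausea or fatigue

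*Combined protocol and SAP*

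**What the plan says.** **Section 6.1 (Dosage).** The paragraph on toxicity opens by sending the reader to Sections 8 and 9 for DLTs and dose changes. It then describes a hold, resumption at a lower dose, and a limit on the number of steps: "A maximum of 2 dose reductions" (340 to 260 to 200 mg/m²) "will be allowed before permanent discontinuation of study drug". The limit is not tied to a type of toxicity. Appendix A has a dosing table for the second step, whose title begins "Imatinib 200mg/m". In the same paragraph, directly after the rule that failure to recover within 14 days ends treatment for good, the text exempts "nausea and fatigue (does not require dose reduction or discontinuation". The exemption has no grade limit.

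**Section 8 (Definition of DLT).** An event must be at least possibly attributable to imatinib. The non-hematologic list includes "Any Grade 3 non-hematologic toxicity with the specific exception of" five entries: ALT, AST, short fever or infection, certain electrolyte disturbances, and amylase or lipase. Nausea and fatigue are not among them.

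**Section 9, item 2 (non-hematological).** "If a patient experiences non-hematologic DLT as defined in Section 8, the treatment will be withheld". If the event resolves within 14 days, treatment may resume at a dose reduced according to Section 6.1. If it does not resolve in that time, the patient must be removed. A further bullet reads "If dose-limiting toxicity recurs in a patient who has resumed treatment at the reduced dose level" and requires removal from protocol therapy.

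**Section 9, item 1 (hematological).** The parallel recurrence bullet carries an additional remark: "maximum of 2 dose reductions allowed), the patient must be removed from protocol therapy". The non-hematologic bullet has no such remark.

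**The concern.** A site that follows one section will treat some patients differently from a site that follows another, although both are adhering to the protocol. In the first situation one reading keeps the patient on a lower dose and the other ends treatment. In the second, one reading leaves the dose unchanged and the other reduces it or ends treatment.

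This is first a matter of patient management. It also touches the analysis, because ending treatment starts the clock toward leaving the study, and the main comparison needs a sample at Month 6. In a study of 20 treated patients at two centers, the rule that decides who stays on treatment should read the same wherever it appears.

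**Working it through.** The check is a comparison of texts. The plan gives no figure for this point, so there is none to reproduce.

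**(a) A non-hematologic DLT that returns at the first reduced level**

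1. The patient has a non-hematologic DLT other than left ventricular dysfunction (which Section 9 treats separately) at 340 mg/m². Sections 6.1 and 9 agree on a hold and resumption at 260 mg/m².
2. The same DLT comes back at 260 mg/m².
3. Section 6.1 has used one of its two reductions, so a step to 200 mg/m² is still open.
4. Section 9, item 2 requires removal from protocol therapy.
5. Reductions available to this patient: 2 under Section 6.1 and 1 under Section 9, item 2.

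Example with a body surface area of 1.70 m², read from the three Appendix A tables:

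- 340 mg/m² table, row from 1.70 upward: 600 mg daily
- 260 mg/m² table, row 1.64 to 1.82: 450 mg daily
- 200 mg/m² table, row 1.63 to 1.87: 350 mg daily

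After the DLT returns at 450 mg, Section 6.1 leads to 350 mg and Section 9 to no drug.

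**(b) Attributable Grade 3 nausea or fatigue**

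1. Section 8: Grade 3, non-hematologic, attributable and not on the exception list, hence a DLT.
2. Section 9, item 2: withhold; if resolved within 14 days, resume at a reduced dose (450 mg in the example); if not resolved, remove.
3. Section 6.1: neither dose reduction nor discontinuation is required (600 mg in the example).
4. Taken action by action:
   - Reduction: Section 9 offers resumption only at a reduced dose, and Section 6.1 says reduction is not required. Opposed.
   - Removal when unresolved at 14 days: Section 9 requires it, and the Section 6.1 exemption lifts it. Opposed.
   - The temporary hold: opposed only if *discontinuation* in the exemption covers a hold. The sentence just before the exemption concerns permanent discontinuation, which points one way. Both sections also use the word for the start of the 14-day hold, which points the other way. The text does not settle it.

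**Precedence.** Section 6.1 refers to Sections 8 and 9, and Section 9 refers back to Section 6.1 for the reduced dose. The references are circular, and no sentence says which section governs.

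**Link to the Month 6 sample.** Section 14 takes a patient off study 30 days after the last dose. Section 15.4 tests the change from baseline to 6 months with a paired t-test. Month 6 is about day 180 (six intervals of 30 days), and 180 − 30 = 150. A patient whose last dose falls before about day 150, visit windows aside, is off study before the Month 6 sample is due. A patient kept on treatment can still provide one.

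**The case against.** The strongest reply on (a) is that a maximum is a ceiling and not an entitlement. Section 9 sets stricter rules elsewhere, for CNS and severe non-CNS hemorrhage and for left ventricular dysfunction, and these read naturally as specific rules beneath a general limit. The non-hematologic recurrence bullet could be another. Section 6.1 also points to Section 9 for dose modifications, and the 200 mg/m² table would still be needed for hematologic cases. This is a fair reading and it softens the conflict. It does not remove it: the text nowhere says that Section 9 prevails, and a reader cannot tell whether the remark present in the hematologic bullet was left out of the other on purpose.

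On (b), the reply is that the exemption qualifies only the preceding rule on permanent discontinuation, and that Section 9 takes its reduction from Section 6.1, where the exemption stands. The first part is a reasonable account of the hold, and for that reason the hold is left open here. It does not cover the rest, because the exemption names dose reduction as well, and Section 9's removal at 14 days still opposes it.

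The principal investigators must be told of every dose modification. That limits uneven practice between the centers, but it does not tell them which rule applies.

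A reader might infer that every second non-hematologic DLT meets opposed instructions. The documents do not support that. Section 9 speaks of a DLT that *recurs* and does not define the word. A different second DLT, or one after a first reduction for a hematologic event, could be handled under Section 9's opening bullet with a further reduction.

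**Conclusion.** Two conflicts stand. The first concerns a non-hematologic DLT, other than left ventricular dysfunction, that comes back at the first reduced level: a second reduction is allowed in one place and removal required in another. The second concerns attributable Grade 3 nausea or fatigue, where the conflict is firm for dose reduction and for removal at 14 days, and depends on the reading for the temporary hold.

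For an affected patient the difference is large: in the example, 350 mg daily against no drug, or an unchanged 600 mg against 450 mg or removal. It can also decide whether a Month 6 pair exists. The conclusion assumes only that the sections are read as printed and that none overrides another.

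A reader might go on to infer a measurable loss of power. With the Section 15.1 inputs (difference 70,000; SD of the difference 75,000 × √(2 × (1 − 0.5)) = 75,000; two-sided alpha 0.01; noncentral t), power is 0.890 with 20 pairs, matching the stated 89%, then 0.866 with 19 and 0.839 with 18. That loss would follow from any dropout, and the documents give no basis for estimating how many patients these rules would affect. It is therefore not evidence of harm from this wording.

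The matter should be fixed, but it does not undermine the design.

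**What to change.** Reconcile Sections 6.1, 8 and 9 so that each point has one rule, worded the same way wherever it appears:

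- **Recurrence.** One rule for a non-hematologic DLT that returns at a reduced dose, with *recurs* defined (the same toxicity or any DLT) and the number of reductions stated in the bullet itself.
- **Nausea and fatigue.** One rule saying whether and at what grade they are exempt, and whether the exemption covers the hold, the reduction, the removal at 14 days, or a combination of these.

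Which rule to adopt is a clinical choice for the investigators.

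The cost is a written amendment approved by all principal investigators, with IRB approval where it significantly affects subject safety (Section 19.1.1). It needs no added patients, visits or procedures.
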